During the enrollment process and after providing consent to participate, subjects will complete a short, online form providing their contact information. Subjects will also be asked to provide the contact information of a spouse, family member or other person in the event the investigator or study personnel lose contact with the subject, so that the subject's status can be determined. The online form is HIPAA-compliant and meets HIPAA regulations for data security. Completion of the form will generate an anonymous study ID associated with that subject and which will be used for other study-related data collection. The study ID does not use any HIPAA-designated identifiers such as birthdate, social security number, etc.

Randomization: The random allocation list will be blocked and stratified by a third-party group or individual. During the trial, only the third-party group and DSMB will have access to the randomization

list, which will be stored on a password-protected computer and/or password-protected file (e.g., REDCap, Excel) by the third-party group or individual. The study personnel will create identical-looking packets with identical-appearing study agents containing a 15-day dosing regimen according to the random allocation list. Study personnel will be blinded to the contents of the distributed packets.

Participant Monitoring and Follow-up: Starting on day 1, and continuing daily for 15 days, subjects will be contacted via e-mail or text message (according to the subject's preference. Messages will include a reminder to take their study medication as scheduled and complete the daily survey (see appendix 12.6.1) each evening prior to going to bed. Subjects will be asked to complete a short questionnaire covering: 1) symptoms they had that day that may be related to COVID-19 (e.g., fever, cough, dyspnea), their frequency and severity; 2) report any other related or non-related medical events; 3) any medications they have taken to relieve symptoms, or other new medications they have not previously reported to study personnel; and 4) any visits they have made to healthcare providers, outpatient centers or hospitals, and details regarding those visits. Subjects will be reminded to contact their primary care physician if they experience symptoms that are worsening or that are concerning to them. For any such contact, they should inform their physician or other healthcare provider that they are enrolled in a clinical trial involving a dietary supplement.

Participants with complete on online PRO-CTCAE questionnaire on days 1, 8 (+1 day), 15 (+1 day), 21 (+1 day), 30, and 60 to monitor for adverse events.

Subjects who do not complete questionnaires will receive a reminder Xe-mails. All patients will be called for a phone interview after 21 days. If subjects cannot be contacted via phone, study personnel will attempt to contact the spouse/family member/friend who is listed as the secondary contact in order to determine the subject's status. A subject will be considered lost to follow-up if their status concerning hospitalization during the study period cannot be verified.

Outcome Assessment and Other Key Variables. Hospitalizations will be determined based on query of subject and/or the subject's secondary contact. The subject's medical records will be requested from the admitting hospital (and discharging hospital, if separate) via a HIPAA authorization.

Additional outcomes will include assessing number of days with fever and to assess symptoms, including dyspnea and fatigue. Questionnaires to assess symptoms will be based on the PRO-CTCAE (see appendix 12.6) (National Cancer Institute, 2020).

Conditions that the CDC defines as being high risk for developing severe COVID-19, and pertinent medications will be recorded. Given the prior safety history of RV and given the potential risks to healthcare workers exposed to COVID-19 patients, we do not intend to obtain laboratory studies as part of this trial.

Assessment for Blinding Integrity and Treatment Adherence. Patients will be asked if they thought they received resveratrol or placebo at 21 (±2) days after enrollment. Patients will be asked report the number of remaining capsules at end of day 16.

4.2 SCIENTIFIC RATIONALE FOR STUDY DESIGN

There is no established standard of care for COVID-19 prior to hospitalization. Therefore, this study seeks to establish superiority of the study intervention over a placebo. Due to the previously established safety and tolerability of the study intervention, limited sample size, and time pressure during the COVID-19 pandemic, no dose-response study will be performed at this time.

4.3 JUSTIFICATION FOR DOSE

STUDY AGENT: RESVERATROL

Human clinical trials of RV have used a wide range of dosages (from 10mg to 5g). RV is generally well tolerated with few side effects reported (notable exception being worse outcome in multiple myeloma treatment given a high (single daily 5g) dosage associated with diarrhea/dehydration/renal injury) (Berman, Motechin, Wiesenfeld, & Holz, 2017). An in vitro study of CoV has shown half maximal inhibitory concentration (IC50) of RV as 5.5 μ g/ml (Zhang, 2015). While RV is well absorbed, there notably is extensive first pass intestinal and hepatic metabolism of RV. In a study of a single 500mg dose of RV, serum plasma concentration of free-RV reached an average of only 71ng/ml while sulfated-RV reached an average 1516 ng/ml and glucuronated-RV reached 4083 ng/ml (Sergides, Chirilă, Silvestro, Pitta, & Pittas, 2016). The in vitro study showing an IC50 of 5.5 μg/ml (5500 ng/ml) cited above referred to unmetabolized RV. It is unclear to what extent sulfated and glucuronated forms of RV would be metabolically active in vivo against CoV. If only the free form RV is metabolically active against CoV it would be difficult to achieve adequate blood levels to accomplish viral inhibition. Recent molecular modelling of RV derivatives support the concept that glucuronated-RV would be biologically active against SARS-CoV2 by inhibition of papain-like protease and RNA-dependent RNA polymerase. Furthermore, the binding affinity of glucuronated-RV was demonstrated to be superior to the free form of RV (Ranjbar, Jamshidi, & Torabi, 2020). Considering that human trials have shown benefit in even small (10mg) dosing of RV (Berman, Motechin, Wiesenfeld, & Holz, 2017) it would be reasonable to hypothesize that sulfated and/or glucuronated RV are (directly or indirectly, see below) biologically active. In vitro studies have demonstrated that glucuronated RV to be comparably biologically active (Lu, et al., 2013). Tissue concentration of RV is not well understood, but one study of the IV volume of distribution suggested significant extravascular distribution, and a mouse study showed preferential accumulation is tissues (Walle, 2011). Furthermore, it has been suggested that human tissue sulfatases and glucuronidases may locally convert the conjugates back to free-RV (Walle, 2011). The half-life of free-RV is measured at 5 hours, while the half-life of sulfated and glucuronated RV are both about 8 hours (Sergides, Chirilă, Silvestro, Pitta, & Pittas, 2016).

The dosing schedule planned for this study is based on attempting to maximize the plasma levels (and presumably tissue levels) of resveratrol in order to attempt to approach or exceed the minimum inhibitory concentration of the resveratrol against SARS-CoV2. There are not any reported toxic plasma levels associated with orally administered resveratrol. The main limiting factor in the dosing is the concern for GI side effects which is infrequent at doses of 1gm or less (Almeida, et al., 2009) (Boocock, et al., 2007) (Brown, et al., 2010). This goal of viral inhibition is in addition to the anti-inflammatory host benefits.

Prior pharmacokinetic studies have consistently shown low plasma levels of unconjugated RV, with substantially higher levels of sulfated-RV and glucuronidated-RV. The Area Under the Curve (AUC) for glucuronidated-RV is inconsistent in the literature. (Boocock, et al., 2007) (Brown, et al., 2010) (Sergides, Chirilă, Silvestro, Pitta, & Pittas, 2016). There is evidence that the glucuronidated-RV is equally biologically active (Lu, et al., 2013). The is also in vivo evidence that sulfated-RV can serve as a reservoir for unconjugated RV via intracellular sulfatases (Patel, et al., 2013).

Estimates of steady state concentration (C_{ss}) are based on prior pharmacokinetic studies of Area Under the Curve (AUC) divided by the dosing frequency planned for this study (C_{ss} =AUC/ τ) noted below (see Table 1). Prior literature has shown a consistent measurement in the measurement of unconjugated RV, but a wide range of measured resveratrol conjugates. Boocock and Brown measured AUC for 0.5, 1.0, 2.5, and 5gm dosages (Boocock, et al., 2007) (Brown, et al., 2010). Sergides measures AUC based on a single 500mg dose (Sergides, Chirilă, Silvestro, Pitta, & Pittas, 2016). Bioavailability of RV Glucuronide from Sergides, et al notably is a magnitude higher than reported by Boocock or Brown. Based on a 1gm dosage every 6 hours, C_{ss} for unconjugated RV will range from 84 ng/ml (Brown), to 91 ng/ml (Boocock), to 70 ng/ml (extrapolated from Sergides). Considering that the RV conjugates are expected to be biologically relevant it worth noting that the cumulative C_{ss} of RV (including unconjugated, sulfonated, & glucuronidated RV) could range from 2638 ng/ml (Brown) to 2708 ng/ml (Boocock), possibly up to 18,500 ng/ml based on extrapolation on the Sergides data.

Assuming RV conjugates are biologically active against SARS-CoV2, the Sergides data suggests that 4gm daily dosing will exceeded the IC50. The Brown and Boocock data suggest that the oral dosing would not exceed the IC50 of coronavirus.

TABLE 1: AUC & estimated Steady State Serum Concentration

	Total Daily dose in gm	unconjugated RV	4'O glucuronide RV	3'O glucuronide RV	Sulfate RV	Cumulative RV Measurements in ng/ml
AUC 1gm (Brow	n)	503	3774	2087	9464	15828
C _{ss} 6hr dosing	4	84	629	348	1577	2638
AUC 1gm (Booc	ock)	544.8	3059	2589	10053	16245.8
C _{ss} 6hr dosing	4	91	510	432	1676	2708
AUC 0.5gm (Bro	wn)	175	1331	875	3558	5939
C _{ss} 6hr dosing	2	29	222	146	593	990
AUC 0.5gm (Boo	ocock)	224	1919	1287	4049	7479
C _{ss} 6hr dosing	2	37	320	216	675	990
AUC 0.5gm (Ser	gides)	154	33	535*	12050	45739
C _{ss} 6hr dosing	2	26		589*	2008	7623

*Sergides did not differentiate glucuronidated RV forms

STUDY AGENT: VITAMIN D3

Vitamin D3 (D3) is a fat-soluble vitamin used in this study to enhance the anti-inflammatory effects of RV. While D3 is known for its role in calcium and phosphorus regulation, there is also evidence that it has roles in immunity, inflammation, and cardiovascular health (Maity, Bora, & Sur, 2018). Vitamin D has a role of providing innate immunity including the production of the antimicrobial cathelicidin in respiratory epithelial cells (Hansdottir, et al., 2008). Supplementation of D3 is associated with a decrease in the incidence of viral respiratory infections (Gysin, Dao, Gysin, Lytvyn, & Loeb, 2016). Specific to this study, D3 has been shown to have a synergistic effect with RV and magnifies RV's effect on the inhibition of IL-6 and TNF- α (Maity, Bora, & Sur, 2018) which may play a significant role in the cytokine storm of COVID-19.

D3 deficiency is common worldwide. D3 levels of 30-50ng/ml can modulate inflammatory activities (Zhang, et al., 2012). A single dose of D3 at 100,000 IU (2500mcg) has been shown to reach a mean concentration of 42 ± 9 ng/ml in healthy volunteers. (Ilahi, Armas, & Heaney, 2008) which would be consistent with a level adequate enough to have anti-inflammatory benefits. Vitamin D toxicity is rate

and has been defined by serum levels of >150ng/ml. A daily dose of up to 10,000 IU per day has been described at the upper limit for supplementation in adults (Holick, et al., 2011). Single doses of up with 2,000,000 units (in an accidental overdose) has been well tolerated (Ouweland, Fleuren, Drabbe, & Vollaard, 2014).

Both treatment group and placebo group will receive a single 100,000 IU D3 to differentiate the effects of RV from potential beneficial effects of D3. The use of D3 will be open label for both groups.

4.4 END OF STUDY DEFINITION

A participant is considered to have completed the study after they have completed a minimum of 7 days of treatment, noting patient will be permitted to discontinue treatment after having 3 days of resolution of fever, fatigure, and dyspnea and they has been followed up with 60 days of enrollment by way of completing the last online survey, exit interview and/or chart review.

The study is considered complete after the last enrolled participant has completed the study.

5 STUDY POPULATION

5.1 INCLUSION CRITERIA

The World Health Organization has categorized baseline severity (see table 1). For this study we will be targeting Mild COVID-19 based on their initial ability to be managed as an outpatient and known estimates for admission rates. Patients who test positive but are asymptomatic (such as being tested for contact tracing) will be excluded from the study as there are no defined estimated for admission rates for asymptomatic patients (patients who become symptomatic can be considered for enrollment).

Furthermore, patients age 45 and greater will be selected for this study due to their higher admission rates. In order to be able to detect a difference in treatment efficacy, a population with a higher admission rate is desirable in order keep the sample size (and its associated cost) down. Noting that, in general, the younger population is more social and may have higher rates of infection, but lower rates of admission including younger age patients in the study would likely skew the population to a low hospitalization rate with resultant difficulty detecting a difference between groups. In addition, in order to avoid unnecessary testing and exposure of healthcare workers to patients with COVID-19, pregnancy will be assessed via self-report of pregnancy potential and report of last menstrual period. The risk of pregnancy will be low in this age group.

Patient must test positive for SARS-CoV2 based on an FDA approved test. Due to low false positive rates and to minimize risk to healthcare providers, minimize the use of PPE and discomfort to the patient, repeat confirmatory testing will not be utilized.

- Outpatients in Central Ohio
- Age ≥45 years
- Mild COVID-19 based on WHO Baseline Severity Categorization (see Table 1)
- Symptom duration \leq 7 days
- Patient must have access to the internet or a smartphone to complete surveys
- English-speaking patients

Disease Severity	Description
SARS-CoV-2 Infection	Positive testing by standard reverse transcription polymerase chain
without Symptoms	reaction (RT-PCR) assay or equivalent test
	No Symptom
Mild COVID-19	Positive testing by standard RT-PCR assay or equivalent test
	• Symptoms of mild illness could include fever, cough, sore throat,
	malaise, headache, muscle pain, gastrointestinal symptoms,
	without shortness of breath or dyspnea
	No clinical signs indicative of Moderate, Severe, or Critical Severity

Table 1: Baseline Severity Categorization

Moderate COVID-19	 Positive testing by standard RT-PCR assay or equivalent test Symptoms of moderate illness, which could include any symptoms of mild illness or shortness of breath with exertion Clinical signs suggestive of moderate illness with COVID-19, such as respiratory rate ≥ 20 breaths per minute, saturation of oxygen (SaO2) >93% on room air at sea level, heart rate ≥ 90 beats per minute No clinical signs indicative of Severe or Critical Severity
Severe COVID-19	 Positive testing by standard RT-PCR assay or equivalent test Symptoms suggestive of severe systemic illness with COVID-19, which could include any symptoms of moderate illness or shortness of breath at rest, or respiratory distress Clinical signs indicative of severe systemic illness with COVID-19, such as respiratory rate ≥ 30 breaths per minute, heart rate ≥ 125 beats per minute, saturation of oxygen (SaO2) <93% on room air at sea level or PaO2/FiO2 <300 mmHg No criteria for Critical Severity
Critical COVID-19	 Positive testing by standard RT-PCR assay or equivalent test Evidence of critical illness, defined by at least one of the following: Respiratory failure defined based on resource utilization requiring at least one of the following: endotracheal intubation and mechanical ventilation, oxygen delivered by high flow nasal cannula (heated, humidified, oxygen delivered via reinforced nasal cannula at flow rates > 20 L/min with fraction of delivered oxygen ≥ 0.5), noninvasive positive pressure ventilation, ECMO, or clinical diagnosis of respiratory failure (i.e., clinical need for one of the preceding therapies, but preceding therapies not able to be administered in setting of resource limitation) Shock (Defined by systolic blood pressure <90mmHg, or diastolic blood pressure <60 mmHg or requiring vasopressors) Multi-organ dysfunction / failure

Source: WHO R&D Blueprint novel coronavirus

5.2 EXCLUSION CRITERIA

- Diagnosed or suspected cognitive impairment that would prevent the patient from cooperating with study procedures, as judged by the screening clinician.
- Asymptomatic patients (e.g. patients who were screened without symptoms but tested positive).
- Known history of cirrhosis, hepatic impairment, or Hepatitis C
- Known of history of renal impairment as measured by an eGFR of < 60 mL/min.
- Patients receiving chemotherapy or who are on chronic immunosuppressants.
- Allergy to grapes or rice.
- Co-morbidities with a high likelihood of hospitalization within 30 days (e.g., current cancer treatment, severe COPD or CHF)
- Currently pregnant

- Hospitalization
- Co-administration of "statins" and PDE-5 inhibitors must be withheld while on study treatment (see section 6.5).
- Due to concerns of patients taking immunosuppressants and drug interactions in medications with a narrow therapeutic index the use of the the following medications will be exclusionary (Blix, Viktil, Moger, & Reikvam, 2010) (Shaito, et al., 2020).

Immunosuppressants			
Generic Name Common Examples			

"Blood Thinners" / NOACs		
warfarin Coumadin		
rivaroxaban	Xarelto	
apixaban	Eliquis	
dabigatran	Pradaxa	

HIV Protease Inhibitors		
atazanavir	Reyataz	
darunavir	Prezista	
fosamprenavir	Lexiva	
indinavir	Crixivan	
lopinavir/ritonavir	Kaletra	
nelfinavir	Viracept	
ritonavir	Norvir	
saquinavir	Invirase	
tipranavir	Aptivus	
atazanavir/cobicistat	Evotaz	
darunavir/cobicistat	Prezcobix	

Immunosuppresants			
Janus Kinase Inhibitors			
tofacitinib	Xeljanz		
Calcineur	in Inhibitors		
cyclosporine	Neoral, Sandimmune, SangCya		
tacrolimus	Astagraf XL, Envarsus XR, Prograf		
mTOR inhibitors			
sirolimus Rapamune			
everolimus	Afinitor, Zortress		
IMDH inhibitors			
azathioprine Azasan, Imuran			
leflunomide Arava			
mycophenolate CellCept, Myfortic			
Bio	Biologics		

abatacept	Orencia	
adalimumab	Humira	
anakinra	Kineret	
certolizumab	Cimzia	
etanercept	Enbrel	
golimumab	Simponi	
infliximab	Remicade	
ixekizumab	Taltz	
natalizumab	Tysabri	
rituximab	Rituxan	
secukinumab	Cosentyx	
tocilizumab	Actemra	
ustekinumab	Stelara	
vedolizumab	Entyvio	
Monoclonal Antibodies		
basiliximab	Simulect	
daclizumab	Zinbryta	
other		
hydroxychloroquine	Plaquenil	
chloroquine	Aralen	

Seizure medications	
carbamazepine	Tegretol
phenobarbital	Luminol
phenytoin	Dilantin
valproate	Depakote

Cardiac medications	
amiodarone	Cardarone, Pacerone
digoxin	Lanoxin
flecainide	Tambocor
sotalol	Betapace

Psychiatric medications		
lithium	Eskalith	

Pulmonary medications		
theophylline	Elixophyllin, Theochron	

Antibiotics	
rifampin	Rifadin, Mycobutin

5.3 LIFESTYLE CONSIDERATIONS

During this study, participants will be asked to:

- Discontinue/avoid any dietary supplements not prescribed by their usual healthcare providers
- Women of child-bearing potential will be asked to take a home pregnancy test (provided) prior to the start of the study intervention and report the results via online survey. They will also be also be asked to use some form of contraception during the 15-days they are on the study treatment.

5.4 SCREEN FAILURES

Screen failures are defined as participants who consent to participate in the clinical trial but are not subsequently randomly assigned to the study intervention or entered in the study. A minimal set of screen failure information is required to ensure transparent reporting of screen failure participants, to meet the Consolidated Standards of Reporting Trials (CONSORT) publishing requirements and to respond to queries from regulatory authorities. Minimal information includes demography, screen failure details, eligibility criteria, and any serious adverse event (SAE).

Individuals who do not meet the criteria for participation in this trial (screen failure) because of a lack of symptoms at the time they tested positive (e.g. tested positive for contact tracing purposes, but was asymptomatic at the time of screen) may be rescreened if symptoms develop. Rescreened participants should be assigned the same participant number as for the initial screening.

5.5 STRATEGIES FOR RECRUITMENT AND RETENTION

An IRB approved HIPAA waiver will allow for recruitment by contacting patients who test positive for SARS-CoV2 and directly providing information about the trial to the potential participant. All potential participants will be screened for capacity to consent by a study clinician.

Retention will be facilitated by daily reminder emails/surveys and phone calls to participants who do not respond to the online survey.

Dose reduction to 1 capsule 4 times per day will be offered to patients considering withdrawing due to GI side effects or who rate their diarrhea as frequently or higher on the PRO-CTCAE 5 point scale.

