6.4 STUDY INTERVENTION COMPLIANCE

Participants will document their compliance daily.

Noting that many patients will have a short duration of symptoms (in order to avoid unnecessary side effects), patients will be allowed to discontinue treatment after a minimum of 7 days if they have been symptom free for 3 days. Completion of a minimum of 7 days of treatment whose symptoms have resolved will be consider compliant with treatment.

In case of a single missed dosage, patient will be asked to divide the 2 missed capsules amongst their next 2 dosages. Patient is not to take more than 3 capsules at a time, and no more than 9 capsules in a day.

At the end of the study, participants will report the number of remaining capsules in their bottles at the end of 15 days.

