7.2 PARTICIPANT DISCONTINUATION/WITHDRAWAL FROM THE STUDY

Participants are free to withdraw from participation in the study at any time upon request. An investigator may discontinue or withdraw a participant from the study for the following reasons:

- Subject withdraws consent
- Subject voluntarily withdraws from treatment
- Subject is unable to tolerate continued study drug administration
- Significant study intervention non-compliance
- Subject experiences a Grade 3 or higher adverse event attributed to the study drug by the investigator
- Subject experiences a Grade 3 or higher clinically significant laboratory abnormality attributed to the study drug by the investigator
- Subject's clinical condition has worsened to be considered "severe" or "critical"
- If the participant meets an exclusion criterion (either newly developed or not previously recognized) that precludes further study participation.
- Subject becomes pregnant
- Subject becomes lost to follow-up

The reason for participant discontinuation or withdrawal from the study will be recorded on the Case Report Form (CRF).

Patients that discontinue/withdraw from the study will continue to be followed for a minimum of 21 days after randomization to assess outcomes/hospitalization rates as allowed.

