8.3.4 TIME PERIOD AND FREQUENCY FOR EVENT ASSESSMENT AND FOLLOW-UP

The occurrence of an adverse event (AE) or serious adverse event (SAE) may come to the attention of study personnel by way of participant online survey results and interviews of a study participant presenting for medical care, or upon review by a study monitor.

All AEs including local and systemic reactions not meeting the criteria for SAEs will be captured on the appropriate case report form (CRF). Information to be collected includes event description, time of onset, clinician's assessment of severity, relationship to study product (assessed only by those with the training and authority to make a diagnosis), and time of resolution/stabilization of the event. All AEs occurring while on study must be documented appropriately regardless of relationship. All AEs will be followed to adequate resolution.

Any medical condition that is present at the time that the participant is screened will be considered as baseline and not reported as an AE. However, if the study participant's condition deteriorates at any time during the study, it will be recorded as an AE.

Changes in the severity of an AE will be documented to allow an assessment of the duration of the event at each level of severity to be performed. AEs characterized as intermittent require documentation of onset and duration of each episode.

Research clinicians will record all reportable events with start dates occurring any time after informed consent is obtained until 7 (for non-serious AEs) or 30 days (for SAEs) after the last day of study participation. At each study visit, the investigator will inquire about the occurrence of AE/SAEs since the last visit. Events will be followed for outcome information until resolution or stabilization.

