10.1.7 CLINICAL MONITORING

Clinical site monitoring is conducted to ensure that the rights and well-being of trial participants are protected, that the reported trial data are accurate, complete, and verifiable, and that the conduct of the trial is in compliance with the currently approved protocol/amendment(s), with International

Conference on Harmonisation Good Clinical Practice (ICH GCP), and with applicable regulatory requirement(s).

• The principal investigator or designee will at least weekly review the results of the patient survey data assess patient's progress and condition.

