12.6 PATIENT SURVEYS

12.6.1 - DAILY QUESTIONNAIRE

Data entered on the form might not be seen by the researchers for several days. If you have concerns about your current condition, call your primary care provider or the Ohio Department of Heath hotline at [name]. If you are having a medical emergency, go to your nearest emergency department or call 911.

When to seek care for COVID-19

If you develop emergency warning signs for COVID-19 get medical attention immediately. Emergency warning signs include*:

Trouble breathing Persistent pain or pressure in the chest New confusion or inability to arouse Bluish lips or face

*This list is not all inclusive. Please consult your medical provider for any other symptoms that are severe or concerning.

For non-urgent questions, more information can be found at: https://www.cdc.gov/coronavirus/2019-ncov/if-you-are-sick/steps-when-sick.html

	These are DRAFT example questions.	
Confidential	Questions will be finalized before patient	
	enrollment.	Resveratroi for COVID-19 Page 1 of 3
Symptom Diary		
Symptom Diary	Note that questions will be formatted for	
	electronic viewing and will have conditional	
Study ID	formatting such that only relevant questions	
	will be visible.	 

Our goal is for you to take 8 capsule divided over the course of the day, such as 2 capsules with each meal (breakfast, lunch, dinner), and again at bedtime. If you miss one dose, you can divide the missed dosage amongst the next 2 dose. For example, if you missed the breakfast dose, you can take 3 with lunch, 3 with dinner, and 2 at bedtime. You should take the capsules with some food or snack. You are more like to have an upset stomach with 3 capsules than 2 capsules. Although you are likely to have no adverse effects either way. If you notice that the capsules give you an upset stomach, be sure to take them with food.

Medication diary [study_id]

Please refer to the paper diary sheet, how many capsules did you take yesterday? (If you took all of 4 doses, you would have taken 8 capsules).

- (	1	~
Ō	5	3
C)	4
C)	5
C)	6
C)	7
C)	8
C)	9
1	14	J_

01

(We understand that remembering to take pills 4 times a day can be difficult, and we understand that some doses may get missed. It is important for us to understand if missed doses will make difference in the results.)

Symptom Diary			
	Yes	No	Unknown
Fever >100.4F (38C)	0	0	0
Subjective fever (felt feverish)	0	0	0
Chills	0	0	0
Muscle aches (myalgia)	0	0	0

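### The reduced dose offered in section 5.5 is not carried into the dosing sections, the missed-dose rule or the draft daily survey, and its symptom trigger has no named questionnaire and no stated review time shorter than weekly

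*Combined protocol and SAP*

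**What the plan says.** The reduced dose appears in one place, section 5.5 of the protocol, under recruitment and retention: "Dose reduction to 1 capsule 4 times per day will be offered to patients considering withdrawing due to GI side effects". A second group is also offered it, those "who rate their diarrhea as frequently or higher on the PRO-CTCAE 5 point scale".

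The other dosing texts describe one regimen only:

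- Sections 6.1.1 and 6.1.2 give 2 capsules 4 times per day, with 120 capsules supplied for 15 days.
- Section 6.4 says that after a single missed dose the "patient will be asked to divide the 2 missed capsules amongst their next 2 dosages". It sets upper limits of 3 capsules at one time and 9 in a day.
- The draft daily questionnaire (12.6.1) tells participants: "Our goal is for you to take 8 capsule divided over the course of the day". Its worked example of a missed breakfast dose is 3, 3 and 2 capsules, and it equates four doses taken with 8 capsules.

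On timing, section 10.1.7 has the principal investigator or a designee "at least weekly review the results of the patient survey data". The daily questionnaire warns participants: "Data entered on the form might not be seen by the researchers for several days". The schema (1.2) provides a phone call when a survey has not been completed within 24 hours. No action is described for a completed survey whose diarrhea answer meets the section 5.5 level.

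**The concern.** A participant who accepts the reduction needs texts that fit it. As drafted, the daily goal and the missed-dose instruction both fit only the dose that the participant has just stepped down from. This touches the risk that the protocol itself puts first: its risk-benefit assessment (2.3.3) names GI upset, with possible dehydration and renal injury.

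Two further gaps follow.

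- **Trigger.** Diarrhea frequency is asked on the same five response levels in the daily survey and in the scheduled PRO-CTCAE. Section 5.5 does not say which one counts, or how soon anyone will look.
- **Adherence data.** No field for the currently assigned dose is described. Four capsules recorded on a day could mean full adherence to a reduced dose or half the doses missed at the full dose.

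**Working it through.** **Plan's own figure.** 2 capsules × 4 per day × 15 days = 120 capsules, which matches the stated supply. The supply is therefore sized for the full dose.

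**Daily goal against reduced dose.**
- Full dose: 2 × 4 = 8 capsules a day. Reduced dose (5.5): 1 × 4 = 4 capsules a day.
- Survey goal ÷ reduced dose = 8 / 4 = 2.
- Apparent adherence of a fully adherent reduced participant, scored against the survey's 8: 4 / 8 = 50%.

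**Missed-dose rule at the reduced dose.** A reduced participant misses 1 capsule, but section 6.4 speaks of 2, one to be added to each of the next two doses. Read literally:

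| Dose missed | That day | Next day |
|---|---|---|
| First | 0 + 2 + 2 + 1 = 5 | 4 |
| Second | 1 + 0 + 2 + 2 = 5 | 4 |
| Third | 1 + 1 + 0 + 2 = 4 | 2 + 1 + 1 + 1 = 5 |
| Fourth | 1 + 1 + 1 + 0 = 3 | 2 + 2 + 1 + 1 = 6 |

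The assigned figure is 4 each day. Nor does the rule adapt on a looser reading, because one missed capsule cannot be split between two doses as whole capsules.

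A related point arises in the same section at the full dose. A missed bedtime dose gives 3 + 3 + 2 + 2 = 10 capsules the next day, above the section's own limit of 9. That also needs reconciling.

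**Review delay for the symptom trigger.** A minimum frequency of once a week allows a delay of up to 7 days, and 7 / 15 = 47% of the course. The documents do not put a number on several days, so a range is shown:

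| Delay | Capsules at full dose | Capsules at reduced dose |
|---|---|---|
| 1 day | 8 | 4 |
| 3 days | 24 | 12 |
| 7 days (worst case) | 56 | 28 |

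The unnamed questionnaire matters here. If the daily item is the trigger, the delay is at most about 7 days from the answer. If only the scheduled PRO-CTCAE counts, an answer on day 8 (+1) read 7 days later is read on day 15 or 16, when treatment is ending.

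**The case against.** The strongest reply is that most of this is silence in an unfinished text. That reply has force on several points, and it rules out some stronger conclusions that a reader might draw.

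- **That reduced participants will be told every day to take 8 capsules.** Not established. The questionnaire is marked as a draft, to be finalized before enrollment, with conditional display of relevant questions. The documents show no reduced-dose version, but they do not show that the final survey lacks one. The front page of the drug diary and the product label cannot be read in the available text.
- **That the review interval contradicts section 5.5.** It does not; this is a timing gap. Weekly is a minimum frequency, and section 8.3.5 provides for ongoing review of adverse events. The survey's warning about delay is a caution to seek care elsewhere, not a review schedule. A participant who says that they are thinking of withdrawing reaches the offer without any survey review.
- **That the limits of 3 and 9 are doses to take.** They are ceilings.
- **That an accepted reduction leads to withdrawal.** Section 7.2 does list "Significant study intervention non-compliance", but as something for which the investigator may withdraw a participant, with no numeric threshold.
- **That section 8.3.4 conflicts with the trigger over diarrhea present before treatment.** The rule "Any medical condition that is present at the time that the participant is screened will be considered as baseline and not reported as an AE" governs adverse event reporting, not dosing, and later deterioration is still recorded.
- **That exposure becomes uninterpretable.** Capsules taken are recorded daily, remaining capsules are reported, and the primary analysis (9.4.2) uses the intention-to-treat population.

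What the reply does not remove is that sections 6.1.1, 6.1.2 and 6.4 are protocol text, not draft survey items. Conditional display is promised for questions; it is not said to cover the dosing text, and no assigned-dose field is described. The 24-hour call does not reach a participant who has completed the survey.

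**Conclusion.** The point holds as an incomplete provision. The reduced dose in section 5.5 is absent from sections 6.1.1, 6.1.2 and 6.4 and from the daily survey as drafted. Followed as written, these give a reduced participant a goal of twice the reduced dose, and a missed-dose rule that yields 5 capsules against 4 after a missed first dose. The symptom trigger has no named questionnaire. It could be read up to 7 days late in a 15-day course; that is a worst case and applies to the symptom trigger only.

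The statistical consequence is limited. The primary intention-to-treat comparison stands. What is lost is the ability to tell an offered reduction from missed doses in the adherence data, where full adherence at the reduced dose reads as 50%.

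This rests on three assumptions: that the survey stays as drafted, that the section 6.4 rule is applied literally, and that no document outside this file, such as the Manual of Procedures mentioned in section 10.1.10, already covers the reduced dose. How many participants would be reduced is not stated, so the overall effect on adherence cannot be sized.

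**What to change.** 1. The sponsor should reconcile sections 5.5, 6.1.1, 6.1.2, 6.4, 10.1.7 and 12.6.1 on the reduced dose, and state which questionnaire, the daily item or the scheduled PRO-CTCAE, carries the section 5.5 trigger. The conflict within section 6.4 after a missed bedtime dose can be settled in the same edit.
2. Before the draft survey is finalized, add a REDCap field holding the currently assigned dose, and use the planned conditional display so that the dosing text, capsule question and missed-dose text agree with it.
3. Report adherence together with that field, so that reductions can be distinguished from missed doses.
4. Set an automated alert to the study clinician when a diarrhea answer meets the section 5.5 level.

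The cost is protocol and survey wording, one field with display logic and one alert, in a system already planned and a survey still in draft. The downside is a few more clinician callbacks. No dose, limit, missed-dose rule or withdrawal rule is proposed here; those are for the sponsor to state.
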